Protocol

1. Project Title:

The effect of hemidiaphragm stimulation during surgery on gene expression and single fiber contractile properties in humans

2. Investigator(s):

[name], PT;
[name], MPH

3. Abstract:

Approximately 10% of the patients who receive mechanical ventilation (MV) experience difficulty weaning, and these patients account for approximately 40-50% of the total MV days. Numerous animal studies have documented that MV induced muscle inactivity leads to diaphragm atrophy, oxidative stress, altered diaphragm gene expression and reduced muscle strength in as little as 6-24 hours. This phenomenon has been termed ventilator induced diaphragm dysfunction (VIDD). Spontaneous breathing for 5 minutes every 6 hours over a 24 hour period of MV support can attenuate VIDD by approximately 50% in a rodent model, indicating that very brief periods of normal diaphragm activity can be protective. Recent human work has documented VIDD (diaphragm muscle fibers atrophying ~ 55%) following approximately 39 hours of controlled MV. Clinical human studies have shown that patients experiencing difficulty weaning from MV have impaired diaphragm performance, consistent with changes seen in VIDD models. Therefore, while there is growing evidence that MV rapidly leads to VIDD in animals and humans, and brief periods of diaphragm activity during MV support can lessen VIDD in a rodent model, there are no data examining strategies to attenuate this problem in humans. We have data examining human diaphragm gene expression (within subjects design) at the beginning and end of ~5 hours of surgery/MV support. The data revealed up regulation of several diaphragm genes controlling ubiquitin mediated catabolic activity and down regulation of genes critical to normal muscle contractile function. We propose to study the effects of periodically stimulating one hemidiaphragm and using the unstimulated hemidiaphragm as a control in a human MV/surgical model. The right or left hemidiaphragm will be stimulated via the corresponding phrenic nerve during surgery depending upon the ease of access. Costal diaphragm muscle samples will be obtained from each hemidiaphragm at the end of surgery. Gene expression, mitochondrial function and single muscle fiber contractile properties in the stimulated and unstimulated hemidiaphragms will be contrasted. This study will provide the first data examining the molecular and contractile effects of increased diaphragm activity during periods of MV/surgery in humans. The results from this research study will help direct efforts to develop rehabilitation interventions in the preoperative and postoperative period aimed at preventing VIDD in humans.

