
animal models and has focused on the dysfunction side of the muscle plasticity continuum, with sparse attention given to measures to reduce VIDD [9-12, 15, 17, 26]. Only two studies have directly studied the impact of MV on human diaphragm structure and none have directly measured muscle contractile performance following periods of MV. Levine's recent report on the effects of 36 hours of MV in humans was discussed earlier. The only other human study used a case control design that qualitatively showed profound diaphragm muscle fiber atrophy in a young child ventilated for 47 days compared to a child ventilated for 3 days [27]. The current evidence indicates that short periods of MV leads to VIDD in animal models and difficult to wean humans clinically demonstrate VIDD. Given the evidence of VIDD, it is clear that mechanistic human data are needed to design strategies to prevent or treat the problem.

In this study, we propose to stimulate either the right or left human hemidiaphragm hourly during routine cardiothoracic (CT) surgery and to obtain diaphragm muscle biopsies from the stimulated and unstimulated hemidiaphragms at the end of surgery for analysis with micro gene arrays, mitochondrial function and single muscle fiber contractile properties. To our knowledge, this project would provide the first simultaneous data on the human diaphragm's gene expression, mitochondrial function and contractile responses to activity during surgery and MV support. This knowledge will be invaluable to developing strategies to protect the diaphragm from the deleterious effects of MV and surgery.

This project will help establish our human diaphragm surgery/MV model, facilitating applications for support from the NIH to study preoperative diaphragm training paradigms and intraoperative pharmacologic interventions.

5. Specific Aims:

Aim 1: Compare the expression of the human diaphragm genes that control energy metabolism, excitation-contraction coupling, contractile proteins and oxidative stress in stimulated and unstimulated diaphragm muscle samples.

Aim 2: Compare the single muscle fiber contractile characteristics (subdivided by muscle fiber type) of stimulated and control diaphragm muscle fibers.

Aim 3: Compare the mitochondrial function of stimulated and control diaphragm muscle fibers.

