We hypothesize that intermittent stimulation of either the right or left human hemidiaphragm during thoracic surgical procedures and lung transplant lasting approximately 5 hours or longer will prevent or attenuate inactivity-induced changes in gene expression, mitochondrial function and single fiber contractile properties as compared to the unstimulated hemidiaphragm.

6. Research Plan:

Subjects:

Patients undergoing regularly scheduled cardiothoracic surgery, including lung transplants, at Shands Hospital at the University of Florida will be recruited to enroll in this prospective study. From each subject an informed consent will be obtained to donate two diaphragm muscle biopsy samples during the surgery.

After recruitment, an initial evaluation consisting of basic demographic information as well as diagnostic information pertaining to the surgery will be performed before the scheduled surgery to search for exclusion factors. In addition, we will track medications, ventilator use, complications, and length of stay during the patient's hospitalization for surgery. Up to 100 subjects will be studied.

Exclusion Criteria:

1. Age < 18 or > 80,
2. history of prior surgery to the diaphragm or pleura;
3. a diagnosis of COPD will be determined from a clinical history consistent with chronic bronchitis and/or emphysema, a long history of cigarette smoking, and pulmonary function tests consistent with irreversible airflow obstruction (FEV1 < 40% predicted, according to European Respiratory Society criteria (1)).
4. a diagnosis of chronic heart failure (NYHA class IV) (2)
5. clinical diagnosis of other lung disease (cystic fibrosis, bronchiectasis, lung cancer; etc.);
6. renal insufficiency (serum creatinine > 1.6 mg/dl);
7. severe hepatic disease (any liver function tests > 1.5 times the upper limit of normal);
8. undernourishment (body mass index < 20 kg/m²),
9. chronic uncontrolled or poorly controlled metabolic diseases (e.g., diabetes, hypo- or hyperthyroidism)
10. orthopedic diseases, suspected paraneoplastic or myopathic syndromes,
11. if in the surgeons' judgment the patients' clinical status warrants, diaphragm stimulation will be stopped and biopsies will not be obtained,
12. items #3 and #5 above will not apply to transplant patients.

Experimental Procedure:

Before the surgery:

A pulmonary function test will be performed to determine whether the subject qualifies for the study.

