The method selected to obtain diaphragm biopsies was designed to minimize the risk of bleeding, phrenic nerve injury, or diaphragmatic impairment. The surgeon will obtain a full-thickness diaphragm sample, approximately 6 mm X 20 mm, from the antero-lateral costal regions of the stimulated and unstimulated hemidiaphragms, shortly before the surgery is completed. By harvesting the diaphragm biopsy from the anterior costal diaphragm, in a region opposite of the phrenic nerve insertion, we will minimize the proximity to phrenic insertion. The wounds will be closed with sutures. The surgeon will place the biopsy samples on ice and hand them to study staff. Tissue samples will be divided using the procedures described below. One part of the sample will be sent to [name]'s laboratory for mitochondrial respiration and gene analysis. One sample will be sent to [name] laboratory (University of Florida, College of Medicine) for RNA analysis. Samples to be analyzed with micro gene array and RNA analysis will be immediately placed in RNAlater solution and stored at -80° C until analysis. Another part of the sample will be sent to [name] laboratory (College of Health and Human Performance, University of Florida) for contractile and fiber type measures. Samples destined for single fiber contractile properties will be placed in a relaxing solution containing 50% glycerol (vol/vol) and stored at 20°C for no more than 4 wk before subsequent analysis. (12) A portion of the tissue samples will be sent to a non-UF investigator, [name] at the University of Arizona for

analysis of muscle titan integrity. After harvest, tissue samples will be coded to protect subject confidentiality and tissue samples will not contain identifying information such as the subject name, medical record are other identifying information. All of the tissue will be consumed during the analysis of the various variables and will not be stored or bank for use outside of this protocol.

In addition we will request the subject's permission to be videotaped for this research project. The process of stimulation of the phrenic nerve and the contraction or movement of the diaphragm muscle will be videotaped during the surgery. A separate consent [Consent to be videotaped and to different uses of the videotape(s)] will be obtained from the subjects.

C. After Surgery:

Data Analysis:

Microarray Analysis:

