The gene micro array analysis will be performed in [name] laboratory (Department of Aging at the University of Florida, College of Medicine). In brief, a U133 plus 2.0 Affymetrix GeneChip or similar product will be used to query the entire human genome (~ 54,000 probes). Total RNA will be harvested for cDNA preparation using protocols and reagents recommended by Qiagen Inc. cDNA will be prepared using protocols recommended by Affymetrix and reagents obtained from Invitrogen. Biotin labeled-cRNA preparation will be accomplished using protocols and reagents recommended by Affymetrix. The labeled-cRNA will be used to interrogate DNA microarrays prepared by Affymetrix. cRNA will be synthesized from cellular RNA from specimens based on protocols and recommendations from the GeneChip manufacturer, Affymetrix.

Single fiber contractile and fiber type measures:

Single fiber contractile and fiber type measures will be done in [name] laboratory (Physiology laboratory at the Center for Exercise Science, University of Florida). [name] laboratory has extensive experience with these techniques (13).

Muscle fibers treatment:

Following collection, muscle fiber bundles will be stretched ~20%, pinned on cork, and placed in a relaxing solution consisting of 59.0 mM potassium acetate, 6.7 mM magnesium acetate, 5.6 mM NaATP, 10 mM EGTA, 2.0 mM dithiothreitol, 15.0 mM creatine phosphate, 1 mg/ml phosphocreatine kinase, and 50 mM imidazole for a total ionic strength of 200 mM at a pH of 7.0 at 5°C and then shipped to [name] laboratory for analysis. The fiber bundles can be stored in relaxing solution for up to 3 weeks before analysis.

Myosin heavy chain concentration and single-fiber gel electrophoresis:

Single fiber segments (~1.5-2.5 mm in length) will be fixed in 4% paraformaldehyde for 30 s and placed on a microscope stage with a CCD camera. The fiber image will be

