mg/ml NTB (nitrotetrazolium blue). Complex II: 4.5 mM EDTA, 10 mM KCN, 0.2 mM phenazine methasulfate, 84 mM succinic acid and 50 mM NTB in 1.5mM phosphate buffer, pH 7.4. Complex IV: 5 mg 3:30-Diamidobenzidine tetrahydrochloride (DAB) dissolved in 9 ml phosphate buffer (0.05 M, pH 7.4), 1 ml catalase (20 µg/ml), 10 mg cytochrome c, and 750 mg sucrose. Complex V: 35 mM Tris, 270 mM glycine, 14mM MgSO₄, 0.2% Pb(NO₃)₂, and 8 mM ATP, pH 7.8. Gels will be washed in distilled water and the bands quantified by digital imaging using a CCD camera. Activity and content will be normalized to muscle weight, mitochondrial DNA content (21) as well as citrate synthase activity (22).

3. Titan analysis: The integrity and phosphorylation of Titan subunits of the sarcomere will be analyzed in [name] laboratory at the University of Arizona. [name] group has extensive experience making this unique measurement and will follow procedures as they have previously published.(25, 26)

Statistical Analysis:

We will use a mixed effects model with random intercept for each subject to evaluate the fixed effects of stimulation and fiber type on single-fiber force mechanics. For other dependent variables (i.e. mitochondrial respiration, RNA, protein quantification), we will test differences between the stimulated and unstimulated tissue samples using paired parametric T tests when the data meet the assumptions of parametric analysis, or non-parametric tests if the data are not normally distributed.

7. Possible Discomforts and Risks:

The risks of diaphragm biopsy include failure of the biopsy site to close, bleeding, phrenic nerve injury, and diaphragm dysfunction. The portion of the diaphragm from which the biopsy is obtained (6 mm by 20 mm section of tissue) will be isolated from the remaining muscle by surgical staples, prior to excision of the full-thickness biopsy sample. The site will also be reinforced with sutures, minimizing the risks of bleeding or failure of the biopsy site to close.

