While human diaphragm biopsies are a relatively new model to study muscle, numerous workers have obtained non-therapeutic, experimental human diaphragm tissue samples during routine surgeries, as proposed in this work (27-35) and no complications were reported. We have recently completed a study in which two diaphragm samples were obtained from 5 subjects at the beginning and end of CT surgery, and there were no intra or postoperative complications associated with the diaphragm biopsies. The addition of indirect phrenic nerve stimulation to the protocol poses no significant risk to the subjects.

Respiratory testing (pulmonary function testing & maximum inspiratory pressure testing) may elicit transient fatigue or shortness of breath that resolves within several seconds of completion. Each training set typically lasts less than 15 seconds, and at least two to three minutes of rest will be provided between trials to minimize feelings of exertion, and perceived exertion will be monitored during training sessions.

This study may include risks that are unknown at this time.

8. Possible Benefits:

There are no direct benefits to the subjects for participating in this study, but our results will lead to a better understanding of how MV affects human diaphragm and may lead to improved clinical care for MV patients. The potential importance of optimizing diaphragmatic function prior to surgery was shown by Hulzebos (2006). These researchers showed that 2 weeks of specific diaphragm training prior to coronary bypass surgery significantly reduced the incidence of post operative pneumonia and duration of hospitalization. The molecular basis of the improved post-operative diaphragmatic function following preoperative conditioning is unknown.

9. Conflict of Interest:

No real or potential conflict of interest exists for any investigator with regard to this research project.

Reference:

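### The plan names no array-specific test: if its RNA sentence covers the ~54,000-probe array, a moderated paired t test with no probe-level rank fallback should be pre-specified, and would matter if only about 5 to 15 pairs are arrayed

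*Combined protocol and SAP*

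**What the plan says.** Section 6, Statistical Analysis, is the only statistical text. It gives single-fiber force a mixed model. For the other dependent variables it says "i.e. mitochondrial respiration, RNA, protein quantification), we will test differences between the stimulated and unstimulated tissue samples using paired parametric T tests" when parametric assumptions are met, "or non-parametric tests if the data are not normally distributed". It does not name the fallback test, and it does not say whether normality is judged probe by probe.

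Section 6, Microarray Analysis, says that a commercial gene chip "will be used to query the entire human genome (~ 54,000 probes" and then describes laboratory steps only. Under Diaphragm Biopsies, the array and the RNA work are listed side by side: "Samples to be analyzed with micro gene array and RNA analysis will be immediately placed in RNAlater solution". Aim 1 is to "Compare the expression of the human diaphragm genes that control energy metabolism, excitation-contraction coupling, contractile proteins and oxidative stress" between the two sides.

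The design is paired within subject: "Costal diaphragm muscle samples will be obtained from each hemidiaphragm at the end of surgery". The only enrolment figure is "Up to 100 subjects will be studied". No minimum, target or number of array pairs is given. Section 7 mentions a completed study in which "two diaphragm samples were obtained from 5 subjects at the beginning and end of CT surgery". That study is cited for biopsy safety, and its comparison is start versus end of surgery.

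**The concern.** Read as covering the array, the stated method has two weaknesses. Both are separate from the question of which error rate is controlled.

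First, an ordinary paired t test estimates each probe's variance from that probe's own pairs. With few pairs this estimate is unstable. Probes with a small SD by chance rise in the ranking, and real changes with a large SD by chance are lost. The other probes carry information on the distribution of variances, and the stated test does not use it.

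Second, an exact rank test has a smallest attainable p-value. A probe sent to that branch can be impossible to call at an array-wide threshold, however large its change.

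At stake is the yield of Aim 1 from tissue that cannot be collected again: subjects give two full-thickness biopsies with no direct benefit to themselves.

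**Working it through.** **Inputs from the documents.** About 54,000 probes; one sample per side per subject; up to 100 subjects; paired t test or an unnamed non-parametric test. The plan states no power, alpha, effect size, SD or multiplicity rule, so it has no figure to reproduce.

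**Assumptions.** Two-sided tests; typical SD of paired log2 differences about 0.4; probe variances drawn from a common prior with d0 = 4 to 10 degrees of freedom; 2% of probes changed (0.02 × 54,000 = 1,080); Benjamini-Hochberg false-discovery rate (FDR) 5% for both methods. Changes in SD units are the log2 change divided by 0.4.

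**Variance instability.** The sample variance over its true value follows chi-square(n-1)/(n-1). Its 95% range is 0.12-2.79 at 5 pairs, 0.30-2.11 at 10, 0.47-1.73 at 20 and 0.74-1.30 at 100.

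**Moderated test.** The variance becomes (d0·s0² + (n-1)·s²)/(d0 + n-1), where s0² is the prior variance, on n-1+d0 degrees of freedom. At a Bonferroni level of 0.05/54,000 = 9.26e-7 and d0 = 4, the critical t, ordinary versus moderated, is 50.4 vs 13.4 at 5 pairs, 11.7 vs 8.7 at 10, 7.1 vs 6.6 at 20 and 5.24 vs 5.22 at 100.

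**Simulated power at 5% FDR, 2% of probes changed.**

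| Pairs | Change, log2 (SD) | d0 | Ordinary | Moderated |
|---|---|---|---|---|
| 5 | 1.0 (2.5) | 4-10 | 0.2% | 48-86% |
| 5 | 0.8 (2.0) | 4 | 0.1% | 0.0% |
| 5 | 0.8 (2.0) | 10 | 0% | 48% |
| 8 | 0.8 (2.0) | 4-10 | 36-43% | 64-88% |
| 8 | 0.4 (1.0) | 4 | 0% | 0% |
| 10 | 0.6 (1.5) | 4-10 | 33-37% | 49-71% |
| 10 | 0.4 (1.0) | 4 | 1-2% | about 0% |
| 20 | 0.4 (1.0) | 4-10 | 51-58% | 55-68% |
| 20 | 0.3 (0.75) | 4 | 21.4% | 20.8% |
| 100 | 0.2 (0.5) | 4-10 | 73-83% | 73-84% |

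The share of false calls averaged near 5% for both tests wherever they made a useful number of calls. Estimating the prior from the data, instead of treating it as known, left the gains unchanged.

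A second grid, with 5% of probes changed, fills in other pair numbers. At 15 pairs, a 1.5 SD change goes from 76% to 82% (d0 = 4) or 88% to 95% (d0 = 10), and a 1 SD change from 40% to 46% or 44% to 58%. At 50 pairs, a 1 SD change goes from 91% to 92% or 98.0% to 98.5%.

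**Rank branch, if it is an exact signed-rank test.** The smallest two-sided p on n pairs is 2^(1-n). Benjamini-Hochberg at 5% can call such a probe only if the number of calls is at least 2^(1-n) × 54,000/0.05.

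- 5 pairs: 0.0625 × 1,080,000 = 67,500, more than the array holds, so impossible.
- 10 pairs: 0.001953 × 1,080,000 = 2,109.4, so at least 2,110.
- 12 pairs: at least 528. 15 pairs: at least 66.
- Bonferroni: 2^(-20) = 9.54e-7 at 21 pairs is still too large; 2^(-21) = 4.77e-7 at 22 pairs is the first to pass.

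At 10 pairs, 2,110 calls is nearly twice the 1,080 probes assumed to be changed. In simulation with a Shapiro-Wilk switch at 0.05, none of the changed probes sent to this branch was detected at 8 or 10 pairs.

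**The case against.** **Few pairs is not in the plan.** This stands. The only planned figure is the ceiling of 100, where the gain is negligible. A reader might infer a small array from the five subjects in Section 7, but they belong to an earlier study with a different comparison. Equally, nothing in the plan sets a minimum or rules out 5 to 15 pairs.

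**The RNA entry may mean single transcripts.** This stands as a possibility. Diaphragm Biopsies lists the array and RNA analysis as two items, and PCR is planned under the mitochondrial measurements. On that reading the array has no stated test at all, so a sentence is still needed.

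**The rank-test fault is inferred.** This also stands. The fallback is unnamed, probe-level switching is not stated, and the 5% FDR is an assumption.

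**Aim 1 names gene groups, so 54,000 may not be the operative number.** This is fair, and no gene count is given. But the rank branch needs a fixed share of the tested probes to be called: 0.001953/0.05 = 3.9% at 10 pairs, whatever their number.

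**Moderation does not always help.** Correct: see the rows at 1 SD or less with d0 = 4. At 5 pairs the large gain depends on a change of 2.5 SD or a strong variance prior.

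**The ordinary paired t test is valid.** Agreed. Moderation is a gain in efficiency. It does not repair a biased test.

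**Conclusion.** The point holds conditionally. The plan states no array-specific test and no number of array pairs. If its RNA sentence governs the array, it forgoes variance sharing and leaves open a fallback that may be unable to call any probe.

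Under the assumed variances, the moderated test gains about 13 to 38 points at 10 pairs for a 1.5 SD change (the extremes 49 - 36 and 71 - 33 across the repeated runs, including one that gave 34-36% for the ordinary test). The gain falls to about 6 to 14 points at 15 pairs and 5 to 10 at 20 pairs for a 1 SD change. At 50 to 100 pairs it is about 0 to 3 points. For changes near 1 SD at 8 to 10 pairs neither test is useful, and with d0 = 4 moderation adds nothing or loses slightly.

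A reader might infer that this trial will lose most of its array power, or that probes will certainly be sent to rank tests. The documents support neither. The SD, prior, effect sizes, proportion changed and FDR are all assumptions. The change is still worth making, because it is cheap and the plan does not exclude the range where it matters.

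**What to change.** In Section 6, Statistical Analysis, take the array out of the sentence on paired and non-parametric tests, and state:

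> Array log2 intensities will be analysed by a linear model with subject as a blocking factor and stimulation as the effect, using empirical-Bayes moderated paired t statistics across all probes. No probe-level switch to a rank test will be made.

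Keep the ordinary paired test for single-transcript PCR variables. Stating the intended number of array pairs in the same place would show how much the choice matters.

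The cost is one sentence and standard software, with no extra tissue, arrays or patients. The method assumes that probe variances share a common prior, which the data can check.

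This change does not supply a multiplicity rule, which is a separate gap. At an assumed per-probe level of 0.05, about 0.05 × 54,000 = 2,700 probes would be called by chance if none had changed, whichever t statistic is used.
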